# 6.2 Pre-screening and Written Informed Consent

The site may pre-screen potential subjects by reviewing medical records to identify the study population. Once identified these subjects are approached for the study and consented. The site may not initiate any study specific (non-standard of care) procedures without first obtaining informed consent

Subjects who pass the initial pre-screening will be asked to sign the study specific IRB approved Informed Consent. A member of the research team will approach the subject to obtain informed consent. The background of the proposed study, the procedure, the follow-up schedule and all potential benefits and risks will be carefully explained to the subject prior to obtaining the potential subject's informed consent. A subject is considered "Enrolled" after signing the study specific Informed Consent and if he/she meets all inclusion and exclusion criteria.

Informed consent will be obtained prior to any study specific screening/baseline tests are performed. This does not include any procedures or tests that are obtained via the standard of care related to the subject's non-study related care, prior to undergoing the index procedure.

#### 6.3 Enrollment

Only subjects who meet the inclusion/exclusion criteria, and provide consent will be eligible to receive the treatment and participate in the study. A subject will be considered officially enrolled only if the subject has signed informed consent, meets all the inclusion and none of the exclusion criteria and is treated with the device.

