
	23. Has one or more stents in the treatment vessel.		
	24. Lacking capacity to provide consent.		
Study Duration / Follow- up Period:	Approximately 2 months enrollment period with observation periods at time of procedure, 30 days post procedure and 6 months post procedure. An interim report will be prepared after 30-day follow-up of all subjects. A final report will be prepared following completion of 6-month follow-up of all subjects.  Subjects will be followed per protocol and institutional standard of care for		
	atherectomy treatment of PAD.		
Analysis Population	The primary analysis will be based on the intent-to-treat (ITT) population.		

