# 5.2 Primary Effectiveness Endpoint

The primary effectiveness endpoint is technical success. The technical success is defined as the ability of the FreedomFlowTM Orbital Atherectomy System to achieve a residual diameter stenosis  $\leq 50\%$  immediately post treatment without adjunctive balloon inflation, as assessed by an independent Angiographic Core Laboratory.

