# 6.5.1 Angiography

At the time of the index procedure, prior to introduction of the Cardio Flow orbital atherectomy device, standard angiography will be performed per the guidelines established by the Angiographic Core Laboratory, to confirm final anatomic eligibility. Subjects who do not meet the final angiographic eligibility criteria, as determined by the investigator at the time of the procedure, will be documented as angiographic screen failures and will not be considered enrolled in the study and no further data will be collected. A subject is considered as "enrolled" after the subject meets all angiographic criteria and a bare-metal atherectomy 0.014" guidewire successfully crosses the target lesion via the true vessel lumen.

Angiography will be performed throughout the procedure to document the treatment outcomes and sent to the sponsor. At a minimum, angiographic images at the following timepoint should be taken.

- Baseline angiography to determine subject's eligibility.
- Post any lesions that are pre-dilated by balloon angioplasty if performed.
- After the Cardio Flow FreedomFlowTM orbital atherectomy treatment session(s).
- Post any adjunctive interventions, e.g. balloon angioplasty and/or stenting, to optimize the outcome or bailout the procedure due to vascular complications.
- Final angiography prior to the end of the procedure.

Up to 3 target lesions are allowed based on the angiographic criteria by this protocol. If 2 or 3 target lesions are selected, the lesion will be numbered based on the anatomic order, i.e. common femoral artery, proximal, middle or distal segment of superficial femoral artery, P1, P2 or P3 segment of popliteal artery, anterior tibial artery, posterior tibial artery, and peroneal artery, regardless of the treatment order.

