#### 8 STATISTICS

This study is a one or two center, prospective, non-randomized single-arm Early Feasibility Study. All clinical endpoints will be summarized with descriptive statistics without hypothesis testing. For continuous variables, the range (minimum, maximum), mean, standard deviation, median, first and third quartiles (Q1 and Q3) may be reported, while for discrete variables, count and percentage will be provided.

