# 12.9 Protocol Deviations / Violations and Medical Emergencies

A protocol deviation or violation is a failure to comply with the requirements of the clinical study as specified in the protocol. Examples of protocol deviations include late visits, missed visits, required follow-up testing not completed. An example of a major protocol violation includes enrollment of a study subject who fails to meet inclusion/exclusion criteria as specified in the protocol. Each investigator shall conduct this clinical study in accordance with the study protocol and any conditions required by the reviewing IRB.

Deviations/violations from clinical protocol requirements will be reviewed and evaluated on an ongoing basis and, as necessary, appropriate corrective actions put into place. See Table 12-1: Reports Required from Investigators to Sponsor for reporting timelines for emergency deviation.

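### Three enrollment definitions and an undefined ITT population leave the technical success denominator open, so a failed device delivery or activation could drop out of it

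*Combined protocol and SAP*

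**What the plan says.** The synopsis, under Analysis Population, states: "The primary analysis will be based on the intent-to-treat (ITT) population". Neither the synopsis nor Section 8 says who belongs to that population. Section 8 adds only that "All clinical endpoints will be summarized with descriptive statistics without hypothesis testing".

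Who is enrolled is stated three times, differently:

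- Section 6.2: a subject is enrolled "after signing the study specific Informed Consent and if he/she meets all inclusion and exclusion criteria". Device use is not mentioned. Inclusion criterion 9 asks that the lesion can be crossed with a wire, which brings 6.2 near to 6.5.1, but 6.2 names no enrolling event.
- Section 6.3: official enrollment is limited to a consented subject who "meets all the inclusion and none of the exclusion criteria and is treated with the device".
- Section 6.5.1: enrollment follows once the angiographic criteria are met and the "guidewire successfully crosses the target lesion via the true vessel lumen". The procedure steps in 6.5.3 place the driveshaft over a wire that is already in position, so this event comes before device use.

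Section 5.2 defines technical success by what the system is able to achieve (residual stenosis of 50% or less), read "immediately post treatment without adjunctive balloon inflation". It gives no rule for a subject in whom the device was never delivered or activated. Nor does the protocol say whether being treated means insertion, activation or a pass through the lesion.

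**The concern.** Sections 6.3 and 6.5.1 cannot be read as successive steps of one definition, because 6.3 makes device treatment a necessary condition. A subject whose lesion has been wired but in whom the driveshaft cannot be delivered or activated is enrolled under 6.5.1 and, on a literal reading, not enrolled under 6.3. If ITT means enrolled subjects and 6.3 governs, ITT becomes a treated-only set, and a failure of the device to reach or work in the lesion need not appear in the primary effectiveness rate.

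The event is foreseeable. The secondary Procedure Success endpoint already has a component for malfunctions that end the procedure early, target lesions are at least 70% stenosed, and this is first-in-human use. Descriptive rates in at most 10 subjects are the study's main output, so one subject can separate a perfect rate from an imperfect one. The denominator should be settled before results are known, not chosen between two sections afterwards.

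**Working it through.** The plan states no rate, power or sample-size derivation to reproduce; the 10 subjects in 4.2 are a cap. The check compares the two denominators.

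**Inputs.** n = wired subjects, taken as 10 from the cap in 4.2. k = wired subjects in whom the device could not be delivered or activated; the documents do not give this, so 0 to 3 is assumed. s = technical successes, assumed. Scoring is per subject.

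**Formula.** With non-delivery scored as failure, 6.5.1 gives s/n. With non-delivery not counted as treatment, 6.3 gives s/(n − k). The second is larger whenever s > 0 and k > 0; with s = 0 both are 0%.

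**Results**, with exact (Clopper-Pearson) 95% intervals:

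| k | s | 6.5.1 | 6.3 | Difference (points) |
|---|---|---|---|---|
| 0 | 9 | 9/10 = 90% (55.5–99.7) | 9/10 = 90% (55.5–99.7) | 0 |
| 1 | 9 | 9/10 = 90% (55.5–99.7) | 9/9 = 100% (66.4–100) | 10.0 |
| 1 | 8 | 8/10 = 80% (44.4–97.5) | 8/9 = 88.9% (51.8–99.7) | 8.9 |
| 2 | 8 | 8/10 = 80% (44.4–97.5) | 8/8 = 100% (63.1–100) | 20.0 |
| 2 | 7 | 7/10 = 70% (34.8–93.3) | 7/8 = 87.5% (47.3–99.7) | 17.5 |
| 3 | 7 | 7/10 = 70% (34.8–93.3) | 7/7 = 100% (59.0–100) | 30.0 |

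**Dependence on the two unstated rules**, for n = 10, k = 1, s = 9:

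| Failed attempt counts as treatment? | Non-delivery scored as | 6.5.1 | 6.3 |
|---|---|---|---|
| No | failure | 9/10 | 9/9 |
| No | missing | 9/9 | 9/9 |
| Yes | failure | 9/10 | 9/10 |
| Yes | missing | 9/9 | 9/9 |

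The sections disagree numerically only in the first row. Under either missing-value row the failed delivery is lost whichever section governs, so aligning enrollment without a scoring rule would not be enough.

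**How likely is k ≥ 1?** For an assumed non-delivery probability p, independent across 10 subjects, the chance is 1 − (1 − p)^10: 40.1% at p = 5%, 65.1% at 10% and 89.3% at 20%. The documents support no particular p.

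**Freedom from MAE.** Suppose 10 are wired, one treated subject has an MAE, and one untreated subject is MAE-free. All wired: 9/10 = 90%. Treated only: 8/9 = 88.9%. The wider set is slightly more favourable here.

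**The case against.** The strongest objection is that the direction of the effect is not in the documents. It needs a narrow reading of *treated* and a failure score that 5.2 does not state. That stands: a reader might infer that 6.3 necessarily inflates technical success, but the second table shows that this holds under only one of four combinations. Section 5.2's framing in terms of what the system can achieve makes that scoring the natural one, without making it a rule.

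Second, a failure to activate would not vanish unseen. Section 6.5.4 has malfunctions recorded, 11.6 has the device returned for analysis, and 12.2 has the adjudicator decide Procedural Success. This is true and limits the harm, but none of it fixes the primary denominator; Procedure Success is secondary and has no stated denominator either.

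Third, every count is assumed, no test is planned, and a disposition listing in so small a study would expose any exclusion. That bears on size, not on the contradiction.

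Two further inferences are tempting and unsupported:

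- That 6.3 would remove a treated subject later found ineligible. No deletion rule is stated, 6.2 also conditions enrollment on eligibility, and 12.9 handles the case as a violation: "An example of a major protocol violation includes enrollment of a study subject who fails to meet inclusion/exclusion criteria".
- That data collection stops for a wired but untreated subject. Section 6.5.1 says of subjects who fail the final angiographic criteria that they "will not be considered enrolled in the study and no further data will be collected". The protocol does not say that this extends to a subject who passed those criteria and was wired.

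**Conclusion.** The point holds in a bounded form. Current text gives three enrollment definitions and an ITT population with no definition. Followed literally, 6.3 yields a treated-only set from which a failed delivery or activation can be absent. If non-delivery is scored as failure and a failed attempt is not treatment, each excluded subject among 10 wired raises technical success by up to 10 points. With no such subject the definitions agree.

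The finding is firm on the wording conflict and conditional on the bias. It affects reported rates and who takes up a place under the cap in 4.2, not any inference. It does not extend to subjects already classed as screening failures under 6.5.2, or to procedures stopped after the device has been used. It should be corrected, because a stated rule can produce a misleading primary rate and the correction is cheap.

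**What to change.** 1. Use one definition in 6.2, 6.3 and 6.5.1: consented, all general and angiographic eligibility criteria met, and guidewire across the target lesion via the true lumen. Delete the device-treatment condition from 6.3.
2. Keep subjects who meet exclusion 19 before driveshaft introduction as screening failures, listed with the reason.
3. In the synopsis and Section 8, define ITT as all enrolled subjects.
4. Score failure to deliver or activate the device as technical failure. Count enrolled subjects with no device attempt (for example, when a sub-intimal wire is suspected only after apparent crossing) as non-successes in ITT and list them with the reason. Add a supplementary technical success rate among subjects in whom device introduction was attempted.
5. Report freedom from MAE on ITT and also on all subjects in whom the driveshaft was introduced.
6. In Section 11, where AE recording now starts with treatment, state when it starts for enrolled but untreated subjects.

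**Cost.** Wording in the synopsis and Sections 6.2, 6.3, 6.5.1, 8 and 11. Technical success may be slightly less favourable. ITT freedom from MAE may be slightly more favourable (9/10 against 8/9 in the assumed case), which the driveshaft-introduced set makes visible. An untreated enrolled subject uses one of the 10 places and is followed at the existing 30-day and 6-month visits; duplex there is specified for the treated lesion, so 6.7 and 6.8 would need a word on what applies.

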# 6.4 Baseline Evaluation (Within 30 Days of Index Procedure)

Subjects that meet the pre-screening eligibility criteria and signed informed consent will have the following collected. These evaluations can occur anytime within 30 days of the procedure to the day of treatment. Only one angiogram is required.

- Demographic Information: race, age, weight, height
- Medical History / Current Status
- Physical Exam and Vital Signs
- Angiogram (recorded and sent to sponsor)
- Duplex Ultrasound (if available, recorded and sent to sponsor)
- Rutherford Classification
- Laboratory Assessments:
  - o CBC, creatinine, and potassium (on day of procedure)
  - o INR & PT if subject is on chronic warfarin therapy (on day of procedure)
  - Urine pregnancy test if female of child-bearing potential (within 7 days of procedure)
  - Hemoglobin, hematocrit, and free hemoglobin (pre-procedure, immediately post-procedure, and at discharge).

- VascuQoL Questionnaire
- Ankle Brachial Index (ABI)
- Concomitant Medications

#### 6.5 Index Procedure

Subjects who meet all of the eligibility criteria will have their scheduled index procedure performed in accordance with physician/investigational site standard practices.

# 6.5.1 Angiography

At the time of the index procedure, prior to introduction of the Cardio Flow orbital atherectomy device, standard angiography will be performed per the guidelines established by the Angiographic Core Laboratory, to confirm final anatomic eligibility. Subjects who do not meet the final angiographic eligibility criteria, as determined by the investigator at the time of the procedure, will be documented as angiographic screen failures and will not be considered enrolled in the study and no further data will be collected. A subject is considered as "enrolled" after the subject meets all angiographic criteria and a bare-metal atherectomy 0.014" guidewire successfully crosses the target lesion via the true vessel lumen.

Angiography will be performed throughout the procedure to document the treatment outcomes and sent to the sponsor. At a minimum, angiographic images at the following timepoint should be taken.

- Baseline angiography to determine subject's eligibility.
- Post any lesions that are pre-dilated by balloon angioplasty if performed.
- After the Cardio Flow FreedomFlowTM orbital atherectomy treatment session(s).
- Post any adjunctive interventions, e.g. balloon angioplasty and/or stenting, to optimize the outcome or bailout the procedure due to vascular complications.
- Final angiography prior to the end of the procedure.

Up to 3 target lesions are allowed based on the angiographic criteria by this protocol. If 2 or 3 target lesions are selected, the lesion will be numbered based on the anatomic order, i.e. common femoral artery, proximal, middle or distal segment of superficial femoral artery, P1, P2 or P3 segment of popliteal artery, anterior tibial artery, posterior tibial artery, and peroneal artery, regardless of the treatment order.

# 6.5.2 Non-Target Vessel/Lesion Intervention

Non-target vessels/lesions can be staged and treated with any commercially available devices greater than 30 days prior to or post the index procedure. If a non-target lesion(s) that locates at the iliac artery or at the femoral artery with a vessel size greater than 5 mm in diameter in the target limb and requires intervention during the index procedure, the lesion(s) MUST be treated with commercially available devices prior to the Cardioflow orbital atherectomy procedure. The CardioFlow orbital atherectomy procedure can be performed ONLY if there are no angiographic complications at the non-target vessel/lesion site and downstream vasculatures and no clinical

adverse event. If any angiographic complication at the non-target vessel/lesion site and downstream vasculatures or clinical adverse event occurred, the subject MUST not proceed to the CardioFlow orbital atherectomy procedure. The subject will be considered as an angiographic screening failure.

## 6.5.3 Cardio Flow FreedomFlowTM Orbital Atherectomy Procedure

Subjects that meet the final angiographic eligibility criteria will have the atherectomy procedure performed according to the Cardio Flow FreedomFlowTM Orbital Atherectomy System Instructions for Use (IFU).

#### Performing the Atherectomy Procedure

Interventionalist will place commercially available 0.014-inch bare-metal atherectomy guidewire through appropriate size introducer sheath based on User Handle model. See IFU provided with the device for details. If this summary differs from the IFU, follow the IFU

Caution: If the physician suspects the guidewire is placed sub-intimally, the atherectomy procedure must be aborted and alternative care performed.

- 1. Once the system is prepped with sterile saline, the distal tip of the User Handle driveshaft can be inserted onto the proximal end of the placed guidewire. Ensure that the guidewire clamp at the back of the User Handle is rotated to the open position to allow the guidewire to exit the User Handle.
- 2. While utilizing imaging technology (fluoroscopy and/or ultrasound), the physician advances the User Handle driveshaft over the guidewire through the introducer sheath and into the patient's vasculature. Continue advancement of the driveshaft and spheres until positioned proximal to the target lesion.

Caution: Verify that the guidewire distal tip is advanced as far distally in patient vasculature as feasible to ensure User Handle driveshaft does not contact the distal tip of the guidewire.

- 3. Once the driveshaft is in the desired location, rotate guidewire clamp clockwise and verify that the guidewire can no longer freely move. Verify that no saline solution is leaking from the guidewire clamp.
- 4. Select the appropriate speed for the vessel size on the touch screen.

Caution: A tight lesion stenosis may require a lower speed, prior to sequential higher speed treatments. Start rotation proximal to a tight lesion stenosis.

5. Fully depress the blue activation button to initiate rotation and maintain selected speed.

6. Once rotation is started, slowly advance the turbine carriage forward and backward through the target lesion.

Warning: Performing atherectomy in the presence of severe arterial spasm can result in vessel dissection or perforation. If severe spasm is observed during treatment with the FreedomFlowTM Atherectomy System, immediately stop driveshaft rotation. If no dissections or perforations are detected, resume treatment only after the vessel spasm has spontaneously resolved or is treated pharmacologically. Prophylactic and episodic antispasm treatment may be administered as described in section 6.5.4 Procedure Medications in this protocol.

Caution: Do not leave the spheres of the driveshaft in one location for more than 5 seconds during rotation. Smooth, slow, continuous motion of the driveshaft forward and backward is recommended.

Caution: Frequent imaging evaluation, such as contrast fluoroscopy and/or ultrasound, should be utilized throughout the treatment procedure to evaluate lesion removal progress and identify potential dissections. The investigational treatment should be discontinued if a dissection is detected

7. To stop driveshaft rotation, release blue activation button.

Caution: If rotation does not cease with release of blue activation button, disconnect the Tubing Set from the User Handle.

- 8. To move the driveshaft to a different target lesion, rotate the guidewire clamp counterclockwise to allow the driveshaft to move independently of guidewire.
- 9. Rotate guidewire clamp clockwise to lock guidewire before activating the driveshaft again.

#### Removal of the User Handle and Driveshaft

- 1. Release blue activation button to stop rotation and retract driveshaft proximal to the lesion using the turbine carriage.
- 2. Rotate guidewire clamp counterclockwise so that User Handle and driveshaft can move independently of guidewire.
- 3. Carefully remove the driveshaft from the guidewire through introducer sheath.
- 4. Turn off peristaltic pump by tapping the OFF icon on the Control Module touch screen.
- 5. Dispose of User Handle and Tubing Set according to standard hospital practice.

## **Changing a Saline Infusion Bag**

To change a saline infusion bag during a procedure, the operation must be paused. If the peristaltic pump door is opened during a procedure, pneumatic power to the User Handle will cease immediately.

- 1. Remove the User Handle and driveshaft from patient (see instructions above).
- 2. Turn off peristaltic pump by tapping the OFF icon on the Control Module touch screen.
- 3. Disconnect current saline infusion bag from IV spike on the Tubing Set and hold the spike upward to prevent the introduction of air.
- 4. Without touching the sterile IV spike tip, insert a new saline infusion bag onto the IV spike and rehang on the IV pole.
- 5. Repeat a complete flush cycle of the User Handle and driveshaft.

#### **6.5.4** Procedure Medications

Warning: Performing atherectomy in the presence of severe arterial spasm can result in vessel dissection or perforation. If severe spasm is observed during treatment with the FreedomFlowTM Atherectomy System, immediately stop driveshaft rotation.

Anti-coagulation medication and loading dose of anti-platelet medications will be given prior to the atherectomy procedure per investigational site atherectomy standard procedure. Antispasmodic medications such as nitroglycerine (200  $\mu$ g intra-arterial (IA) bolus; up to 3000  $\mu$ g per subject) or papaverine (300  $\mu$ g IA bolus) may be administered. To avoid frequent IA bolus injections, the following solution (500 ml normal saline with 3000  $\mu$ g heparin, 3000  $\mu$ g nitroglycerin and 2.5 mg Cardizem) can be infused intra-arterially at a rate of 6 mL/min. All medications administered for this study should be recorded in the subject's medical record.

During the procedure, any device malfunction and device/procedure related adverse events, including anaphylaxis to medications or device components will be monitored and recorded.

